2.6.3 Handling of missing values/censoring/discontinuations

Missing data for ASAS 20 response for data up to Week 12 will be handled by multiple imputation technique as defined in [Section 2.5.3](#).

2.7 Analysis of secondary efficacy objective(s)

Refer to [Table 1.2-1](#) of Section 1 for the list of secondary objectives.

2.7.1 Secondary endpoints

All the secondary efficacy evaluation will be performed on FAS population.

Refer to [Table 1.2-1](#) of Section 1 for the list of secondary endpoints.

2.7.2 Statistical hypothesis, model, and method of analysis

The following hypotheses will be tested for secondary variables. All secondary endpoints will be tested exploratively outside the confirmatory framework:

- H_{3a} : secukinumab 300 mg treatment group is not different to placebo group with respect to ASAS 40 response at Week 12
- H_{3b} : secukinumab 150 mg treatment group is not different to placebo group with respect to ASAS 40 response at Week 12
- H_{4a} : secukinumab 300 mg treatment group is not different to placebo group with respect to BASDAI 50 response at Week 12
- H_{4b} : secukinumab 150 mg treatment group is not different to placebo group with respect to BASDAI 50 response at Week 12
- H_{5a} : secukinumab 300 mg treatment group is not different to placebo group with respect to spinal pain (VAS) response at Week 12
- H_{5b} : secukinumab 150 mg treatment group is not different to placebo group with respect to spinal pain (VAS) response at Week 12
- H_{6a} : secukinumab 300 mg treatment group is not different to placebo group with respect to SPARCC enthesitis index at Week 12
- H_{6b} : secukinumab 150 mg treatment group is not different to placebo group with respect to SPARCC enthesitis index at Week 12
- H_{7a} : secukinumab 300 mg treatment group is not different to placebo group with respect to HAQ-DI[©] at Week 12
- H_{7b} : secukinumab 150 mg treatment group is not different to placebo group with respect to HAQ-DI[©] at Week 12
- H_{8a} : secukinumab 300 mg treatment group is not different to placebo group with respect to FACIT-Fatigue[©] score at Week 12
- H_{8b} : secukinumab 150 mg treatment group is not different to placebo group with respect to FACIT-Fatigue[©] score at Week 12
- H_{9a} : secukinumab 300 mg treatment group is not different to placebo group with respect to ASAS Health index at Week 12
- H_{9b} : secukinumab 150 mg treatment group is not different to placebo group with respect to ASAS Health index at Week 12
- H_{10a} : secukinumab 300 mg treatment group is not different to placebo group with respect to ACR 20 response at Week 12
- H_{10b} : secukinumab 150 mg treatment group is not different to placebo group with respect to ACR 20 response at Week 12

Analysis of secondary endpoints:

- **ASAS 40 at Week 12**

Response to ASAS 40 at Week 12 will be analyzed using a logistic regression model with treatment and concomitant MTX intake status as factors. The Odds ratio, 95% confidence interval (CI) and p-value will be presented comparing secukinumab to placebo.

- **BASDAI 50 at Week 12**

BASDAI 50 response is defined as at least a 50% improvement (decrease) in total BASDAI score, as compared to the Baseline total BASDAI score.

Response to BASDAI 50 at Week 12 will be analyzed using a logistic regression model with treatment and concomitant MTX intake status as factors. The Odds ratio, 95% confidence interval (CI) and p-value will be presented comparing secukinumab to placebo.

- **Spinal pain (VAS) at Week 12**

The patient's assessment of back pain will be performed using a 100 mm VAS ranging from no pain to unbearable pain.

The mean change from baseline of spinal pain at Week 12 will be analyzed by using an ANCOVA model with treatment group, visit and concomitant MTX intake status, as factors and baseline measurement in VAS as continuous covariate. The adjusted (LS) mean difference will be calculated as a point estimate together with the corresponding 95% confidence interval and p-value.

- **SPARCC enthesitis index at Week 12**

The SPARCC enthesitis index focuses on the clinical evaluation and validation of 16 defined sites.

The mean change from baseline of SPARCC enthesitis index at Week 12 will be analyzed by using an ANCOVA model with treatment group, visit and concomitant MTX intake status, as factors and baseline SPARCC index as continuous covariate. The adjusted (LS) mean difference will be calculated as a point estimate together with the corresponding 95% confidence interval and p-value.

- **Physical function index (HAQ-DI[©]) at Week 12**

Refer to Section 2.11

- **FACIT-Fatigue[®] score at Week 12**

Refer to Section 2.11

- **ASAS Health Index at Week 12**

Refer to Section 2.11

- **ACR 20 response at Week 12**

Response to ACR 20 at Week 12 will be analyzed using a logistic regression model with treatment and concomitant MTX intake status as factors. The Odds ratio, 95% confidence interval (CI) and p-value will be presented comparing secukinumab to placebo.

Summary statistics will include relative and absolute frequencies for the binary variable (ASAS 40, BASDAI 50 and ACR 20) and the number of patients (N), minimum, mean, median and maximum for the continuous variable (VAS, SPARCC, etc.,) for each treatment group and by visit. Graphical representation will also be performed.

2.7.3 Handling of missing values/censoring/discontinuations

Missing data for ASAS 40, BASDAI 50 and ACR 20 for data up to Week 12 will be handled by multiple imputations.

Continuous variables (Spinal pain (VAS), SPARCC enthesitis index, HAQ-DI[®], FACIT--Fatigue[®] score and ASAS Health index) will be analyzed using a mixed-effects repeated measures model (MMRM) which is valid under the missing at random assumption. For analyses of these parameters, if all post-Baseline values are missing then these missing values will not be imputed and this patient will be removed from the analysis of the corresponding variable, i.e. it might be that the number of patients providing data to an analysis is smaller than the number of patients in the FAS.

2.8 Safety analyses

All the safety analysis will be performed on the Safety set.

Summaries may be performed separately for the initial (Week 1-12) and entire treatment periods.

The analyses of the follow-up period will be limited to summaries for treatment-emergent adverse events, and serious adverse events.

Safety analyses will be performed on treatment received or actual treatment as described below:

The actual treatment or treatment received for summaries of safety data will differ to the treatment assigned at randomization only if a subject received the wrong treatment during the entire study.

For those patients who did not receive the randomized treatment, i.e. who received erroneously the wrong treatment at least once, an additional AE listing will be prepared displaying which events occurred after the treatment errors and also the relationship with study drug.

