1.1 Study design

This is a 52-week, randomized, double-blind, double-dummy, placebo-controlled, multicenter study to assess the efficacy of secukinumab 150 mg or 300 mg in patients with AxPsA who have had an inadequate response to two different NSAIDs. The study will consist of two treatment periods; a double-blind placebo-controlled period from Baseline to Week 12 followed by a double-blind secukinumab treatment period from Week 12 to Week 52.

The schematic of study design is given in Figure 1.1 below.

Planned number of patients and randomization

A total of 495 patients (165 patients per group) will be recruited to compensate dropouts and protocol violators.

Patient eligibility will be assessed during a maximum screening period of 8-weeks. At Baseline, all patients whose eligibility is confirmed will be randomized in a 1:1:1 ratio to secukinumab 150 mg, secukinumab 300 mg or placebo. At Week 12, patients randomized to placebo at Baseline will be re-randomized (1:1) to active treatment with secukinumab 150 mg or secukinumab 300 mg.

Group 1: secukinumab 150 mg

Treatment Period 1

secukinumab 150 mg (1 × 1.0 mL prefilled syringes (PFS)) + placebo (1 × 1.0 mL PFS) at Baseline, Week 1, 2, 3 and 4, then 4 weeks later at Week 8.

Treatment Period 2

secukinumab 150 mg (1 × 1.0 mL PFS) + placebo (1 × 1.0 mL PFS) administered every 4 weeks from Week 12 to Week 52 (last dose on Week 48).

Group 2: secukinumab 300 mg

Treatment Period 1

secukinumab 300 mg (2 × 1.0 mL PFS) administered at Baseline, Week 1, 2, 3 and 4, then 4 weeks later at Week 8.

Treatment Period 2

secukinumab 300 mg (2 × 1.0 mL PFS) administered every 4 weeks from Week 12 to Week 52 (last dose on Week 48).

Group 3: placebo

Treatment Period 1

placebo (2 × 1.0 mL PFS) administered at Baseline, Week 1, 2, 3 and 4, then 4 weeks later at Week 8.

Treatment Period 2

secukinumab 150 mg (1 × 1.0 mL PFS) + placebo (1 × 1.0 mL PFS) administered every 4 weeks from Week 12 to Week 52 (last dose on Week 48), OR

secukinumab 300 mg (2 × 1.0 mL PFS) administered every 4 weeks from Week 12 to Week 52 (last dose on Week 48).

[figure not shown]
Patients, investigator staff, persons performing the assessments and data analysts will remain blinded to the identity of the treatment from the time of randomization until database lock. No stratification at randomization will be performed.

Primary analysis time point

The primary and key secondary analyses will be performed at Week 12.

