2.2 Analysis sets

The following analysis sets will be used in this trial:

Randomized set: The randomized set will be defined as all patients, who were randomized.

Unless otherwise specified, mis-randomized patients (mis-randomized in IRT) will be excluded from the randomized set.

Mis-randomized patients are defined as those patients, who were mistakenly randomized into the IRT prior to the site confirming all eligibility criteria had been met and to whom no study medication was given. Mis-randomized patients are treated as screen failures.

Any in-eligible patient, who has been randomized and treated during the study, should be part of Randomized Set and Safety Set but excluded from FAS.

Full analysis set (FAS): The FAS will be comprised of all patients from the randomized set, to whom study treatment has been assigned. Following the intent-to-treat principle, patients will be evaluated according to the treatment assigned to at randomization.

Per-protocol set: This set includes all patients, who completed the study without a major protocol deviation.

Safety set: The safety set includes all patients, who took at least one dose of study treatment during the treatment period. Patients will be evaluated according to treatment received.

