2.4 Treatments (study treatment, rescue medication, concomitant therapies, compliance)

2.4.1 Study treatment / compliance

Study Treatment

The summaries by treatment will be performed by the actual treatment received (as follows) or treatment sequence for each treatment period.

Randomized treatment:

- AIN457 300 mg
- AIN457 150 mg
- Placebo

Treatment sequence:

- AIN457 300 mg
- AIN457 150 mg
- Placebo to AIN457 300 mg
- Placebo to AIN457 150 mg

The analysis of study treatment data will be based on the safety set. The number of active and placebo injections will be summarized by treatment group up to Week 12 and Week 52.

Duration of exposure

The duration of exposure to study treatment will also be summarized by treatment group. In addition, the number and percentage of patients with cumulative exposure levels (e.g. any exposure, ≥ 1 week, ≥ 2 weeks, ≥ 3 weeks, ≥ 4 weeks, ≥ 8 weeks, etc.) will be presented.

Duration of exposure for secukinumab groups will be defined as the time from first dose of study treatment to the time of treatment end for each treatment period. Duration of exposure for the placebo group will be defined as the time from first dose of placebo treatment to the time of treatment end in treatment period 1 and the time from first dose of active treatment to the time of treatment end in treatment period 2.

For patients who discontinue, this will be the patient's last visit in the corresponding treatment period.

Duration of exposure (years) = duration of exposure (days) / 365.25

Duration of exposure (100 patient years) = duration of exposure (years) / 100

The analyses of duration of exposure described above will be done for the entire study treatment periods.

Compliance

Compliance will be calculated based on documented study drug administrations and syringe counts and displayed by treatment group.

Compliance is expected to be 100%, unless temporary interruption is needed for safety reasons. Compliance will also be assessed by a Novartis monitor using information provided by the authorized site personnel.

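### The safety rule for actual treatment is tied to the whole study, so a patient misdosed throughout Period 1 but dosed correctly in Period 2 stays in the assigned column of the Day 1–Week 12 tables

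*SAP*

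**What the plan says.** - **Principle.** Section 2.2 defines the safety set as those who took at least one dose and adds: "Patients will be evaluated according to treatment received".
- **Operational rule.** Section 2.8 says how actual treatment is decided. It "will differ to the treatment assigned at randomization only if a subject received the wrong treatment during the entire study".
- **Partial errors.** For patients "who received erroneously the wrong treatment at least once, an additional AE listing will be prepared" (section 2.8). Nothing there moves such patients between columns of the summary tables.
- **Design.** Section 1.1 says that "patients randomized to placebo at Baseline will be re-randomized (1:1) to active treatment with secukinumab 150 mg or secukinumab 300 mg" at Week 12. From then on secukinumab is the correct drug for every patient.
- **Tables concerned.** The overview of safety analyses at the end of section 2.8.4.2 has a separate row for Day 1 to Week 12. It plans crude and exposure-adjusted rates for AEs, SAEs and AESIs, and crude rates for drug-related AEs and notable vital sign, ECG and laboratory values.
- **Exposure summaries.** Section 2.4.1 states: "The summaries by treatment will be performed by the actual treatment received (as follows) or treatment sequence for each treatment period".

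**The concern.** A rule that ignores isolated dosing errors and reclassifies only patients who were wrongly treated throughout is a sensible convention when each patient has one assignment for the whole trial. Here placebo patients have two assignments, and the placebo assignment ends at Week 12. If the test is the entire study, a complete error in Period 1 is cancelled by correct dosing in Period 2.

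Day 1 to Week 12 is the only time in which safety on secukinumab can be set beside safety on placebo. An event on secukinumab in such a patient would be counted in the placebo column, and the patient's exposure would be counted as placebo time. In the opposite case, a patient assigned secukinumab but given placebo throughout Period 1 stays in the secukinumab column. Neither case touches efficacy, which is analysed by randomized treatment.

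**Working it through.** The plan gives no figure to reproduce, because this is a classification rule. The check applies the rule of section 2.8 to the dosing schedule of section 1.1.

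**Dosing occasions, placebo group**
- Period 1: "placebo (2 × 1.0 mL PFS) administered at Baseline, Week 1, 2, 3 and 4, then 4 weeks later at Week 8". That is Baseline and Weeks 1, 2, 3, 4 and 8, so 6 occasions.
- Period 2: "administered every 4 weeks from Week 12 to Week 52 (last dose on Week 48"). That is Weeks 12, 16, …, 48, so (48 − 12)/4 + 1 = 10 occasions.
- Total: 6 + 10 = 16.

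**The case.** A placebo patient receives secukinumab at all 6 Period 1 occasions and then the re-randomized dose at all 10 Period 2 occasions.
- Share of Period 1 doses that were wrong: 6/6 = 100%.
- Share of all study doses that were wrong: 6/16 = 37.5%.
- Share of study time: 12/52 = 23%.

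The patient received no placebo as treatment in Period 1, but the error did not last the entire study. The condition fails and the patient is tabulated as placebo for Day 1 to Week 12.

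**Does other text override the rule?**
- Section 2.1 notes that a patient's group can depend on the analysis period and on whether efficacy or safety is assessed. It sets no rule for errors.
- Section 2.4.1 groups exposure data by actual treatment or sequence within each period. It covers exposure and compliance, and it too sets no rule for errors.
- Section 5.4.3 splits events and exposure by treatment when a patient switches. Its example is a change from placebo to 150 mg with no dosing error.
- Section 5.7 lists administration of the wrong study drug as a deviation (TRT03). The consequence is exclusion from the per-protocol set, with no change of safety column.

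None of these displaces the explicit condition in section 2.8.

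**Size.** With the planned 165 patients per group, and assuming that all enter the safety set, one patient is 1/165 = 0.61 percentage points and two are 2/165 = 1.21. The shift in an event rate arises only if the patient has that event. For a rare AESI with a single case, in such a patient, the placebo rate reads 1/165 = 0.61%. With the patient classified by drug received it would be 0/164 = 0%, and the case would appear as 1/166 = 0.60% in the secukinumab column.

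**The case against.** The strongest reply is that this is a loose phrase with almost no practical effect. Six wrong doses out of six, followed by correct dosing, is improbable in a blinded trial randomized through IRT. Such a case would also be visible: section 2.3.1 tabulates protocol deviations and assigns them to Period 1 or Period 2, and section 2.8 adds the AE listing. Sections 2.1 and 5.4.3 suggest that the authors think in periods anyway. All of this stands, and it limits the severity. It does not remove the point, because a listing and a deviation table do not change the counts or denominators of the safety tables.

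Some stronger readings are tempting, and the SAP does not support them:
- **That section 2.8 contradicts section 2.2.** Section 2.2 states a principle and section 2.8 defines the term. The definition is too coarse for two periods, which is different from a contradiction.
- **That section 2.4.1 contradicts section 2.8 or already requires a per-period variable for dosing errors.** It covers exposure and compliance, and the list that follows its sentence begins with the randomized treatments.
- **That the rule generally biases safety comparisons towards no difference.** This can happen when placebo and secukinumab are confused. It does not follow when a 150 mg patient receives 300 mg, since any extra events would then be counted under 150 mg and would not shrink its difference from placebo. Nor does the SAP plan formal safety testing against placebo.
- **That an identical patient who leaves before Week 12 would certainly be reclassified.** That needs the entire study to mean the patient's own participation, which the SAP does not say.

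**Conclusion.** The point holds in a limited form. As worded, the rule leaves a patient who was misdosed at every Period 1 dose and dosed correctly in Period 2 under the assigned arm in the Day 1–Week 12 safety tables. Correct Period 2 dosing is a necessary condition. A patient who is also wrongly dosed throughout Period 2 meets the rule as it stands and is moved.

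The SAP gives no expected number of such patients. I assume that it is at or close to zero; a range of 0 to 2 would mean 0 to 1.2 percentage points of a 165-patient column, and only for events that those patients have. That is negligible for common AEs and noticeable only for a rare AESI. The primary and key secondary analyses are unaffected. Severity is minor. The reason to act is that the rule gives the wrong column by construction in the only placebo-controlled period, and that correcting it costs almost nothing.

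**What to change.** In section 2.8, replace the whole-study condition with a per-period one: *for each treatment period, actual treatment differs from the treatment assigned for that period only if the patient received the wrong treatment at all administrations in that period.*

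Then:
- Use this variable for both events and exposure in the Day 1–Week 12 tables, so that numerators, denominators and patient-time agree.
- Carry it into the split of events and exposure by treatment already shown in section 5.4.3 for the entire treatment period.
- Keep the additional AE listing for partial errors. A patient wrongly dosed at 5 of 6 Period 1 occasions would still be tabulated as assigned. That keeps the present convention of not reclassifying on partial errors.

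The cost is one sentence and one derived treatment variable per period. No data collection, sample size or efficacy analysis changes. The change is best made before unblinding.

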2.8.1 Adverse events (AEs)

The crude rates of treatment emergent adverse events (i.e. events started after the first dose of study treatment or events present prior to the first dose of study treatment but increased in severity based on preferred term, and events until 12 weeks after last dose of study treatment) will be summarized by primary system organ class and preferred term.

In addition, exposure time-adjusted incidence rates including 95% confidence intervals will be provided for the entire treatment period to adjust for differences in exposure. A graphical display of the crude rates and exposure-adjusted incidence rates will be presented for all AEs and serious AEs by system organ class.

Adverse events will be summarized by presenting, for each treatment group, the number and percentage of patients having at least one AE, having an AE in each primary system organ class and having each individual AE (preferred term). Summaries (crude rates only) will also be presented for AEs by severity and for study treatment related AEs. If a particular AE 'severity' is missing, this variable will be listed as missing and treated as missing in summaries. If a subject reported more than one adverse event with the same preferred term, the adverse event with the greatest severity will be presented. If a subject reported more than one adverse event within the same primary system organ class, the subject will be counted only once with the greatest severity at the system organ class level, where applicable.

Separate summaries will be provided for

- adverse events suspected to be related to study drug by the investigator
- deaths
- serious adverse events
- adverse events leading to discontinuation
- adverse events leading to temporary dose interruption.
- adverse events of special interest

Adverse events will also be reported separately by SMQ according to MedDRA, using a narrow search. The MedDRA version used for reporting the study will be described in a footnote.

Follow-up period summaries will be done for all patients in follow-up.

A listing of non-treatment emergent adverse events will be done. These adverse events occurred before the first dose of the study treatment. The crude rates will be provided without treatment information.

For SAEs occurred during screening a listing will be prepared for all patients screened including screening failures.

Algorithms for date imputations will be provided in Programming Specifications.

For legal requirements of ClinicalTrials.gov and EudraCT, two required tables on treatment-emergent adverse events which are not serious adverse events with an incidence greater than 2% and on treatment emergent serious adverse events and SAE suspected to be related to study treatment will be provided by system organ class and preferred term on safety set population.

If for a same patient, several consecutive AEs (irrespective of study treatment causality, seriousness and severity) occurred with the same SOC and PT:

- a single occurrence will be counted if there is ≤ 1 day gap between the end date of the preceding AE and the start date of the consecutive AE
- more than one occurrence will be counted if there is > 1 day gap between the end date of the preceding AE and the start date of the consecutive AE

For occurrence, the presence of at least one SAE / SAE suspected to be related to study treatment / non SAE has to be checked in a block e.g., among AE's in a ≤ 1 day gap block, if at least one SAE is occurring, then one occurrence is calculated for that SAE.

The number of deaths resulting from SAEs suspected to be related to study treatment and SAEs irrespective of study treatment relationship will be provided by system organ class and preferred term.

